Every 10 days	0	0.0%
Every 2 weeks	0	0.0%
Monthly	0	0.0%
Frequency of infusions/injections 6 months after resumption of prophylaxis		
2x per day	0	0.0%
Daily	0	0.0%
Every 2 nd day	0	0.0%
Every 3 rd day	0	0.0%
3x per week	0	0.0%
2x per week	0	0.0%
Weekly	0	0.0%

Every 10 days	0	0.0%
Every 2 weeks	0	0.0%
Monthly	0	0.0%

Data source: DHR from the start of data collection accompanying the application to approximately 6 months prior to the date of the final report required by the G-BA resolution for AbD
Acronyms: SD: standard deviation; SHL: standard half-life; EHL: extended half-life; PD: plasma-derived

Figure 1 Histograms of ABR for Roctavian and SoC Cohorts

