4. STUDY OBJECTIVES AND ENDPOINTS

The aim of this non-interventional study is to evaluate the overall effectiveness and safety of Roctavian compared to SoC hemostatic prophylaxis treatments for PwSHA.

The specific objectives are listed below. All objectives will compare Roctavian and SoC with exogenous FVIII or emicizumab, unless otherwise noted.

Table 1: Objectives and Endpoints

[figure not shown]
Objectives	Endpoints
Primary	
To compare the annualized bleeding rate for treated bleeds.	
 Bleeding events requiring treatment with exogenous FVIII
Secondary	
To compare the annualized bleeding rate for major, life threatening, and joint bleeds.	
 Major bleeding events Life-threatening bleeding events Bleeding events occurring in the joint
To compare the proportion of people with zero bleeds for treated, major, life threatening, and joint bleeds.	
 Bleeding events requiring treatment with exogenous FVIII Major bleeding events Life-threatening bleeding events Bleeding events occurring in the joint
To compare the use of hemostatic medications.	
 Prophylactic hemostatic treatments On-demand hemostatic treatments
To compare joint health, quality of life, and pain.	
 Hemophilia Quality of Life assessment (Haemo-QoL-A) Hemophilia Joint Health Score (HJHS) Brief Pain Inventory-Short Form (BPI-SF)
To compare safety events of interest.	
 All cause death Hemophilia-related death Adverse events leading to hospitalization or death Targeted adverse events of development of FVIII inhibitors, thromboembolic events, new malignant neoplasms, and severe liver disease (liver failure or cirrhosis)
To describe time to resumption of prophylactic treatment among persons administered Roctavian.	
 Resumption of prophylactic hemostatic treatments

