Adverse events leading to hospitalization and/or death	Medical event leading to hospitalization and/or death	✓	Follow-up (inclusive of index)	Ongoing	
The DHR captures information on medically relevant events including allergic reactions, thromboembolic events, thrombotic microangiopathy, malignant neoplasm, autoimmune disease, sensory paresthesia, infusion/hypersensitivity reaction, complications of immunosuppression and other with a free text field to specify the other category. For each event, the connection to hemophilia treatment (yes/no/unknown) is also recorded, along with serious consequences due to the event (hospitalization, death, none or unknown).
 
Event recorded as leading to hospitalization and/or death will be analyzed both for any reason (regardless of relation to hemophilia treatment) and related to hemophilia treatment. (See limitations of interpretation of events regardless of relationship to hemophilia treatment in Section 10.5).
 
Hospitalizations are defined as a participant having been admitted to the hospital for inpatient care, either to the inpatient ward or to the emergency room for observation and/or treatment that would not have been appropriate in the physician’s office or outpatient setting.

Variable	Description	Captured in DHR	Time period for Analysis	Entry into DHR	Operational notes including Relevant Data Fields in DHR
Targeted Adverse Events					
Development of FVIII inhibitors	Positive inhibitor tests and/or a positive test and the requirement for ITT	✓	Follow-up (inclusive of index)	Ongoing	Based on recording of the DHR variables for positive inhibitor tests after enrollment in the DHR, or use of immune tolerant therapy (ITT). See Table 4 and SAP for additional information on definition for positive inhibitors based on 2 positive tests or 1 test and use of ITT.
Thromboembolic events	Occurrence of a thromboembolic event related to treatment	✓	Follow-up (inclusive of index)	Ongoing	Derived based recording of medically relevant event of thromboembolic event in the DHR that has been identified as connected to hemophilia treatment. Occurrence of thromboembolic events regardless of relationship to treatment will also be described, but not compared. (See limitations of interpretation of events regardless of relationship to hemophilia treatment in Section 10.5)

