Descriptive statistics will be used to summarize the absolute and change from baseline at the time of an assessment for the total and domain scores for the Haemo-QoL-A and the BPI-SF. For the BPI-SF the pain interference and pain intensity scores will be taken as the domains. A repeated measurement analysis model will be used to compare the changes in scores between the treatment groups. Participants with an evaluable baseline score and at least one evaluable post-baseline score will be required for the specific analysis be included in the change from baseline analyses.

In addition, responder analyses will be considered for improvement and deterioration for the BPI-SF pain interference and pain intensity scales. The BPI-SF pain intensity score will be defined as the Question 5 “average pain”. The BPI-SF pain interference score will be defined as the average to all 7 subitems of Question 9 (9A to 9G).

All analysis details and scoring methods will be described in the SAP. It is expected that no missing data will be imputed.

All PROs comparisons will be interpreted after 3 years of follow-up, or latest available follow-up score if a full 3 years of follow-up is not available.

10.3.7.5. Objective: To compare safety events of interest.

Safety events outlined in [Table 8](#) will be described in each cohort. Summaries of the proportion, event rate, and incidence rate of each of the safety events among all participants by cohort will be provided. Safety events will be described from index through follow-up. All participants will be included in analyses of event and incidence rates, while analyses of the proportion of participants will only include those participants with follow-up for the full time over which the proportion is calculated. Safety outcomes will be compared as relative risks based on the incidence of an event for analyses of the treatment policy estimand and as incidence rate ratios censoring a participants person time at the time of the event for analyses of the hypothetical estimand.

10.3.7.6. Objective: To describe time to resumption of prophylactic treatment among participants administered Roctavian

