Hemophilia-related death	Yes	
 Reason for resignation Cause of death Date of retirement 	
 If reason for resignation from DHR is "deceased" and cause of death is captured as "hemophilia-related" 	All available follow-up
AEs leading to hospitalization and death	Yes	
 Medically relevant events in this reporting period Relation to hemophilia treatment Serious consequences due to relevant events 	
 Identified if serious consequences due to relevant events = "hospitalization" or "death"² Events will be analyzed both for any reason (regardless of relation to hemophilia treatment) and related to hemophilia treatment 	All available follow-up
Development of FVIII inhibitors	Yes (calculated)	
 Inhibitor tests against FVIII/FIX positive in this reporting period Date of the inhibitor test Titer Test assay used 	
 If inhibitor tests against FVIII/FIX were performed during the reporting period, participants with a positive test will be identified Based on any recording of the DHR variables for inhibitors developed during the reporting period, positive inhibitor tests during the reporting period, or use of ITT (occasion = "ITT") Titer (BU/ml) 0.0-1000.0 	All available follow-up

Variable	Captured in DHR	DHR data field name(s)	Operational definition and calculation of outcome measures	Timepoints for data collection
		
 Occasion 		
Thrombo-embolic events	Yes	
 Other relevant event Relation to hemophilia treatment 	
 Thromboembolic events connected to hemophilia treatment will be identified if other relevant event = “thromboembolic event” and relation to hemophilia treatment = “yes” 	All available follow-up

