AEs leading to death – connected to hemophilia treatment	0	0.0%	0	0.0%	0.0000	0.00	0	0.0%	0	0.0%	0.0000	0.00
Development of FVIII inhibitors	0	0.0%	0	0.0%	0.0000	0.00	0	0.0%	0	0.0%	0.0000	0.00
Thromboembolic events – any cause	0	0.0%	0	0.0%	0.0000	0.00	0	0.0%	0	0.0%	0.0000	0.00
Thromboembolic events – connected to hemophilia treatment	0	0.0%	0	0.0%	0.0000	0.00	0	0.0%	0	0.0%	0.0000	0.00
Malignant neoplasms	0	0.0%	0	0.0%	0.0000	0.00	0	0.0%	0	0.0%	0.0000	0.00
Severe liver disease – any cause	0	0.0%	0	0.0%	0.0000	0.00	0	0.0%	0	0.0%	0.0000	0.00
Severe liver disease – connected to hemophilia treatment	0	0.0%	0	0.0%	0.0000	0.00	0	0.0%	0	0.0%	0.0000	0.00

Data source: DHR from the start of data collection accompanying the application to approximately 6 months prior to the date of the final report required by the G-BA resolution for AbD

Acronyms: SoC: standard of care; AE: adverse event; FVIII: coagulation factor VIII

Note: Std. diff. examines the balance of covariate distribution between groups, with a value >0.1 indicating some imbalance between groups and >0.25 indicating poor balance.

Table 16 Safety Outcomes for Roctavian and SoC Cohorts

Unadjusted Regression Model

Measures	Regression coefficient	95% Confidence Limits		r ²	p-value
		Lower Limit	Upper Limit		
All cause death	0.00	0.00	0.00	0.00	0.0000
Hemophilia-related death	0.00	0.00	0.00	0.00	0.0000
AEs leading to hospitalization – any cause	0.00	0.00	0.00	0.00	0.0000
AEs leading to hospitalization- connected to hemophilia treatment	0.00	0.00	0.00	0.00	0.0000
Development of FVIII inhibitors	0.00	0.00	0.00	0.00	0.0000
Thromboembolic events – any cause	0.00	0.00	0.00	0.00	0.0000
Thromboembolic events – connected to hemophilia treatment	0.00	0.00	0.00	0.00	0.0000
Malignant neoplasms	0.00	0.00	0.00	0.00	0.0000
Severe liver disease – any cause	0.00	0.00	0.00	0.00	0.0000
Severe liver disease – connected to hemophilia treatment	0.00	0.00	0.00	0.00	0.0000

IPTW-Adjusted Regression Model

Measures	Regression coefficient	95% Confidence Limits		r ²	p-value
		Lower Limit	Upper Limit		
All cause death	0.00	0.00	0.00	0.00	0.0000
Hemophilia-related death	0.00	0.00	0.00	0.00	0.0000
AEs leading to hospitalization – any cause	0.00	0.00	0.00	0.00	0.0000
AEs leading to hospitalization- connected to hemophilia treatment	0.00	0.00	0.00	0.00	0.0000
Development of FVIII inhibitors	0.00	0.00	0.00	0.00	0.0000
Thromboembolic events – any cause	0.00	0.00	0.00	0.00	0.0000

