Thromboembolic events – connected to hemophilia treatment	0.00	0.00	0.00	0.00	0.0000
Malignant neoplasms	0.00	0.00	0.00	0.00	0.0000
Severe liver disease – any cause	0.00	0.00	0.00	0.00	0.0000
Severe liver disease – connected to hemophilia treatment	0.00	0.00	0.00	0.00	0.0000

Data source: DHR from the start of data collection accompanying the application to approximately 6 months prior to the date of the final report required by the G-BA resolution for AbD

Acronyms: AE: adverse event; FVIII: coagulation factor VIII

Note: Negative binomial regression models are used for events that can occur multiple times; Log binomial regression models are used for events that occur once.

Table 17 Free Text Safety Events for Roctavian and SoC Cohorts

Measures	Roctavian Cohort		SoC Cohort	
	N=		N=	
	N	(%)	N	(%)
Free Text Safety Event				
Safety event 1	0	0.0%	0	0.0%
Safety event 2	0	0.0%	0	0.0%
Safety event 3	0	0.0%	0	0.0%
Safety event 4	0	0.0%	0	0.0%

Data source: DHR from the start of data collection accompanying the application to approximately 6 months prior to the date of the final report required by the G-BA resolution for AbD
 Acronyms: SoC: standard of care

Table 18 Time to Resumption of Prophylactic Treatment for Roctavian Cohort

Measures	Roctavian Cohort	
	N=	
	N	(%)
Participants who resumed prophylactic treatment	0	0.0%
Time to resumption of prophylactic treatment (days)		
Mean	0.00	
SD	0.00	
Median	0	
Q1	0	
Q3	0	
Min	0	
Max	0	
Number of infusions/injections 3 months after resumption of prophylaxis		
SHL		
Mean	0.00	
SD	0.00	
Median	0	
Q1	0	
Q3	0	
Min	0	
Max	0	
EHL		
Mean	0.00	
SD	0.00	
Median	0	
Q1	0	

Q3	0
Min	0
Max	0
Emicizumab	
Mean	0.00
SD	0.00
Median	0
Q1	0
Q3	0
Min	0
Max	0
PD	
Mean	0.00
SD	0.00
Median	0
Q1	0
Q3	0
Min	0
Max	0
Number of infusions/injections 6 months after resumption of prophylaxis	
SHL	
Mean	0.00
SD	0.00
Median	0
Q1	0
Q3	0
Min	0
Max	0
EHL	
Mean	0.00

SD	0.00
Median	0
Q1	0
Q3	0
Min	0
Max	0
Emicizumab	
Mean	0.00
SD	0.00
Median	0
Q1	0
Q3	0
Min	0
Max	0
PD	
Mean	0.00
SD	0.00
Median	0
Q1	0
Q3	0
Min	0
Max	0
Total FVIII dose 3 months after resumption of prophylaxis	
Mean	0.00
SD	0.00
Median	0
Q1	0
Q3	0
Min	0
Max	0

Total FVIII dose 6 months after resumption of prophylaxis		
Mean	0.00	
SD	0.00	
Median	0	
Q1	0	
Q3	0	
Min	0	
Max	0	
Frequency of infusions/injections 3 months after resumption of prophylaxis		
2x per day	0	0.0%
Daily	0	0.0%
Every 2 nd day	0	0.0%
Every 3 rd day	0	0.0%
3x per week	0	0.0%
2x per week	0	0.0%
Weekly	0	0.0%

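### As printed, the safety shells give no modelled estimate for AEs leading to hospitalization or death combined, or for fatal AEs; recurrent safety events get count models where the protocol states relative risks

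*Protocol*

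**What the plan says.** **The outcome.** Protocol section 4 (Table 1) lists a single compared safety item: "Adverse events leading to hospitalization or death". Protocol Table 8 (section 7.2.5.7) keeps it together: "Event recorded as leading to hospitalization and/or death will be analyzed both for any reason", and also when related to treatment. The register field behind it records "serious consequences due to the event (hospitalization, death, none or unknown". SAP Table 5 (section 7.4.3) has one variable. Its rule begins "Identified if serious consequences due to relevant events" and accepts either hospitalization or death. SAP 7.9.4.5 says the Table 5 safety events will be reported for both cohorts, and it compares safety outcomes with IPTW-weighted models.

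**The shells (SAP 12.1).** Table 15 splits the item into four rows: hospitalization and death, each for any cause and when connected to treatment. The last of these is "AEs leading to death – connected to hemophilia treatment". Table 16, which holds the regression estimates, has the two hospitalization rows, ending with "AEs leading to hospitalization- connected to hemophilia treatment", and then moves straight to FVIII inhibitors. This is so in both the unadjusted and the IPTW-adjusted panel.

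**The effect measure.** Protocol 10.3.7.5: "Safety outcomes will be compared as relative risks based on the incidence of an event for analyses of the treatment policy estimand". SAP 7.9.4.5, under the same estimand, assigns negative binomial models to outcomes that can recur. The note to Table 16 repeats this: "Negative binomial regression models are used for events that can occur multiple times; Log binomial regression models are used for events that occur once".

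**The concern.** The text and the shells describe different deliverables for a prespecified safety comparison. If the shells are populated as they stand, the outcome named in the objective has no estimate and no confidence interval. The same holds for its fatal component, including deaths from AEs attributed to treatment. For a one-time gene therapy compared with ongoing prophylaxis, that subset is of direct interest.

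The effect measure is also unsettled. The protocol compares how many participants are affected, whereas the SAP's count model compares how many events occur. With a target of only 67 participants in the Roctavian Cohort, a few people with repeated events could move the second measure and leave the first unchanged. Both choices would otherwise be made by the programmer once data exist.

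**Working it through.** The plan gives no figure for this outcome, so there is nothing to reproduce. The check is a comparison of rows, followed by arithmetic on the two effect measures.

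**Step 1. Where each piece appears.**

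| Item | SAP Table 5 | Table 15 (weighted %, p-value, standardized difference) | Table 16 (estimate, 95% limits) |
|---|---|---|---|
| Combined, any cause and connected | yes | no | no |
| Leading to hospitalization, any cause and connected | part of combined | yes | yes |
| Leading to death, any cause and connected | part of combined | yes | no |
| All-cause death | yes | yes | yes |
| Hemophilia-related death | yes | yes | yes |

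**Step 2. Can another modelled row stand in?** All-cause death is taken from the reason for leaving the register and does not record relation to treatment. Hemophilia-related death is defined in protocol Table 8 as death due to the disease. Neither isolates a fatal AE connected to treatment, so that subset has no modelled row.

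**Step 3. What a combined row could add.** This is an illustration with invented counts. It assumes that only one consequence is stored per event, that no participant is counted twice, and that the denominators are the planned 67 and 330.
- Hospitalization row alone: (6/67)/(30/330) = 0.99.
- Adding 2 fatal AEs per cohort: (8/67)/(32/330) = 1.23.
- Adding 3 fatal AEs per cohort: (9/67)/(33/330) = 1.34.

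If the register lets a fatal AE carry both consequences, fatal AEs with an admission are already in the hospitalization row and the gap shrinks.

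**Step 4. Count ratio against relative risk.** With equal follow-up, the count ratio equals the relative risk times the ratio of mean events per affected participant. Invented example: 4/67 against 20/330 affected, with 9 and 24 events.
- Relative risk: (4/67)/(20/330) = 0.99.
- Mean events per affected participant: 9/4 = 2.25 and 24/20 = 1.2, a ratio of 1.875.
- Count ratio: (9/67)/(24/330) = 1.85.

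**Step 5. The same contrast under a negative binomial model.** With mean m = rate × 3 years and dispersion k, the probability of at least one event is p(m) = 1 − (1 + km)^(−1/k). The assumed SoC rates are 0.05 to 0.4 per year and k runs from near 0 to 4; neither range is in the documents. For example, with a rate of 0.1, k = 1.5 and a rate ratio of 2, p(0.6)/p(0.3) = 0.348/0.219 = 1.59. Over the whole grid:
- a rate ratio of 2.0 corresponds to a relative risk between 1.25 and 1.86;
- a rate ratio of 1.5 corresponds to a relative risk between 1.15 and 1.45.

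The two measures come close only when events are rare.

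**The case against.** A reader might infer that the combined outcome is never computed. The documents do not support that: SAP Table 5 defines it, and SAP 7.9.4.5 commits to reporting and comparing the Table 5 events. The fault is a mismatch between shells and text, in a SAP that protocol 10.3 says will be finalized before the first data cut.

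A reader might also infer that a fatal treatment-related AE drops out of the adjusted comparison, so that the more lethal treatment could look safer. Table 15 contradicts this. It has rows for fatal AEs, any cause and connected, with IPTW-weighted percentages, p-values and standardized differences. Table 16 models all-cause death, so a death recorded in the register enters an adjusted estimate whatever its relation to treatment. In the Step 3 example, 2/67 against 2/330 is a ratio of 4.9 and would be visible in Table 15.

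Further points carry weight. The documents do not say that only one consequence can be stored per event. Fatal AEs may be so few that a modelled estimate says little; SAP 7.9.4.5 foresees this with a Firth-corrected logistic model. Secondary p-values are nominal (SAP 7.9). One-time outcomes keep log binomial relative risks, and the protocol itself uses rate ratios for the hypothetical estimand. Table 15 also prints weighted percentages, from which a crude risk ratio follows.

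These points limit the size of the problem but do not remove it. None supplies a modelled estimate for the combined outcome or for treatment-connected fatal AEs, and none reconciles protocol 10.3.7.5 with SAP 7.9.4.5.

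**Conclusion.** The point holds in two limited parts. First, the shells as printed omit the combined row from Tables 15 and 16 and the fatal-AE rows from Table 16. A prespecified compared outcome and its fatal component therefore have no planned estimate or confidence interval in the shells. What is missing is the modelled effect; the descriptive and weighted reporting of the components is there. Second, for recurrent safety outcomes under the treatment policy estimand, the SAP uses a count model where the protocol states a relative risk.

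The numerical size cannot be taken from the documents. The composite ratios of 1.23 and 1.34 depend on invented counts and an unstated storage rule, and show only that a hospitalization-only row can differ from the combined one. The ratio of 1.85 against 0.99 also uses invented counts and says nothing about the width of a negative binomial confidence interval. The range of 1.25 to 1.86 depends on the assumed rates and dispersion. The study's primary comparison is unaffected, but the point should be settled before the SAP is finalized.

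**What to change.** 1. Add the combined hospitalization-or-death outcome, for any cause and treatment-connected, to Tables 15 and 16 as the compared outcome. List its components beneath it and add the AE-leading-to-death rows to Table 16.
2. State that an event counts if either consequence is recorded, so that the result does not depend on how the register stores the field.
3. For the treatment policy estimand, report the first-occurrence relative risk stated in protocol 10.3.7.5, and keep the negative binomial rate ratio as supplementary.
4. State that participants who die count as having completed observation. Protocol 10.3.7.5 restricts proportion analyses to participants with full follow-up, and death ends follow-up under protocol 10.3.2.2. Read literally, the restriction could exclude the fatal cases.
5. Label each Table 16 estimate as a risk ratio, rate ratio or odds ratio. The present single column of regression coefficients would mix all three if the Firth-corrected model is used.

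The cost is a few shell rows, some labels and short wording changes in SAP 7.9.4.5 and protocol 10.3.7.5. The data are already planned for collection.

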12.2. Haemo-QoL-A Scoring

Haemo-QoL-A

The following questions ask how hemophilia and its treatment affect your life. Please take your time and answer all of the questions. There are no right or wrong answers. Please read each question carefully and select one response for each question. If you are unsure about how to answer a question, choose the one response that best represents your opinion.

The first set of questions asks about how **hemophilia** affects your **day-to-day activities**. Think about the **past 4 weeks** when answering these questions.

Please circle the best answer:

		None of the time	A little of the time	Some of the time	A good bit of the time	Most of the time	All of the time
1.	Loss of joint mobility affects how I walk.	0	1	2	3	4	5
2.	It is hard for me to climb the stairs.	0	1	2	3	4	5
3.	It is easy for me to perform daily activities.	0	1	2	3	4	5
4.	I am unable to leave the house because of my hemophilia.	0	1	2	3	4	5
5.	I have to adjust my activities because of pain.	0	1	2	3	4	5
6.	I am able to complete household tasks.	0	1	2	3	4	5
7.	It is easy for me to lift heavy objects.	0	1	2	3	4	5
8.	I depend on others to carry out activities around the home.	0	1	2	3	4	5
9.	I am able to participate in sports.	0	1	2	3	4	5
10.	I have difficulty traveling because of my hemophilia.	0	1	2	3	4	5
11.	I am afraid of being far from a health care center with emergency care facilities.	0	1	2	3	4	5

Please continue ➡

The next set of questions asks about how **hemophilia** affects your **mood and feelings**. Think about the **past 4 weeks** when answering these questions.

Please *circle* the best answer:

		None of the time	A little of the time	Some of the time	A good bit of the time	Most of the time	All of the time
12.	I am hopeful about the future.	0	1	2	3	4	5
13.	I worry about accidents.	0	1	2	3	4	5
14.	I am afraid of being hit or bumped.	0	1	2	3	4	5
15.	I feel less confident than others.	0	1	2	3	4	5
16.	I enjoy life.	0	1	2	3	4	5
17.	I feel much older than my years.	0	1	2	3	4	5
18.	I am afraid of internal bleeding.	0	1	2	3	4	5
19.	I am in control of my life.	0	1	2	3	4	5
20.	I feel like I'm taking a risk when I do things	0	1	2	3	4	5
21.	I feel frustrated because I can't do what I want to do.	0	1	2	3	4	5
22.	Because of my hemophilia, I have difficulty planning for the future.	0 5	1 4	2 3	3 2	4 1	5 0

Please continue ➡

Now we would like to ask you about how **hemophilia** affects your **work or school life, family life and social life**. Think about the **past 4 weeks** when answering these questions.

Please circle the best answer:

		None of the time	A little of the time	Some of the time	A good bit of the time	Most of the time	All of the time
23.	I worry about finding or losing a job.	0	1	2	3	4	5
24.	I worry about missing work or school because of my hemophilia.	0	1	2	3	4	5
25.	I experience restrictions at work or school.	0	1	2	3	4	5
26.	I feel like a burden to my family.	0	1	2	3	4	5
27.	I worry about having children.	0	1	2	3	4	5
28.	Hemophilia interferes with my relationships with my friends.	0	1	2	3	4	5
29.	I worry about not being able to provide for my family.	0	1	2	3	4	5
30.	I am afraid to go to crowded places like concerts or bars for fear of being bumped or injured.	0	1	2	3	4	5
31.	I feel different from others because of my hemophilia.	0	1	2	3	4	5
32.	I feel I have the same opportunities to succeed in life as others.	0	1	2	3	4	5
33.	Others treat me differently.	0	1	2	3	4	5
34.	I feel I can carry out a normal life like the rest of society.	0	1	2	3	4	5
35.	Hemophilia interferes with my ability to have an intimate relationship with another person.	0	1	2	3	4	5
36.	I am afraid of having a bleed in public.	0	1	2	3	4	5

Please continue ➡

The following questions ask about your experiences with your **hemophilia treatment**. Think about the **past 4 weeks** when answering these questions.

Please circle the best answer:

		None of the time	A little of the time	Some of the time	A good bit of the time	Most of the time	All of the time
37.	My hemophilia treatment interferes with my daily activities.	0	1	2	3	4	5
38.	My infusions for hemophilia are stressful.	0	1	2	3	4	5
39.	I worry about the safety of my treatment.	0	1	2	3	4	5
40.	I worry about being treated by health care providers who do not know how to treat hemophilia.	0	1	2	3	4	5
41.	I worry about the availability of hemophilia products.	0	1	2	3	4	5

© 2003 MEDTAP® International and Bayer Biological Products
All rights reserved. Do not duplicate or distribute without permission.

SCORING MANUAL FOR THE HAEMO-QOL-A

Items are answered on a 6-point Likert-type scale, ranging from 0 (None of the time) to 5 (All of the time). Higher scores mean better HRQL or less impairment for a particular subscale.

Recoding items

Some items are positively worded and some are negatively worded. Negatively worded items should be reverse scored so that higher scores reflect better quality of life. The item scores of negatively worded items should be subtracted from 5. For example: Question 1 is a negatively worded item so it should be scored:

$$(5 - \text{Question 1}) = \text{score of reverse scored Question 1.}$$

The positively worded items are the following: 3, 6, 7, 9, 12, 16, 19, 32, and 34. All other items are negative and should be reverse scored.

Scoring

For the Haemo-QoL-A subscales [physical functioning, role functioning, worry, consequences of bleeding, emotional impact (formerly: positive affect), treatment concern], scores are computed by averaging across the items within a subscale. The range of subscale scores is 0 to 5; higher scores mean better HRQL or less impairment for a particular subscale.

To calculate the Haemo-QoL-A total score, sum the value of the individual subscales (do not sum all the individual items). The range of total scores is 0 to 30; higher scores mean better HRQL or less impairment.

For both total and subscale scores, use the formula below to transform raw scores to a 0 to 100 scale. Higher scores will be indicative of better HRQL.

Missing Items

For the subscale analyses, if < 50% of the scale items are missing, the scale should be retained with the mean scale score of the items present used to impute a score for the missing items. If \geq 50% of the items are missing, no scale score should be calculated, the subscale score should be considered missing. If a subscale score is missing, the Haemo-QoL-A total score cannot be calculated

Haemo-QoL-A Scoring Manual

Items by subscale:

SAS Variable Name	Number	Scoring
Physical Functioning		
rHQ3	1	Reverse
rHQ4	2	Reverse
HQ5	3	
rHQ7	5	Reverse
HQ8	6	
HQ9	7	
rHQ10	8	Reverse
HQ12	9	
rHQ14	10	Reverse
Role Functioning		
rHQ6	4	Reverse
rHQ21	17	Reverse
rHQ25	21	Reverse
rHQ26	22	Reverse
rHQ31	26	Reverse
rHQ33	28	Reverse
rHQ37	31	Reverse
rHQ39	33	Reverse
rHQ45	36	Reverse
rHQ46	37	Reverse
rHQ48	38	Reverse
Worry		
rHQ28	23	Reverse
rHQ29	24	Reverse
rHQ30	25	Reverse
rHQ32	27	Reverse
rHQ34	29	Reverse
Consequences of Bleeding		
rHQ15	11	Reverse
rHQ17	13	Reverse
rHQ18	14	Reverse
rHQ19	15	Reverse
rHQ22	18	Reverse

Haemo-QoL-A Scoring Manual

rHQ24	20	Reverse
rHQ36	30	Reverse
Emotional Impact		
HQ16	12	
HQ20	16	
HQ23	19	
HQ38	32	
HQ43	34	
rHQ44	35	Reverse
Treatment Concern		
rHQ49	39	Reverse
rHQ51	40	Reverse
rHQ52	41	Reverse

Haemo-QoL-A Scoring Manual

Scale	Average the Item Values	Lowest/Highest Possible Raw Scores	Range
Physical functioning	$\frac{(1+2+3+5+6+7+8+9+10)}{9}$	0, 5	5
Role functioning	$\frac{(4+17+21+22+26+28+31+33+36+37+38)}{11}$	0, 5	5
Worry	$\frac{(23+24+25+27+29)}{5}$	0, 5	5
Consequences of bleeding	$\frac{(11+13+14+15+18+20+30)}{7}$	0, 5	5
Emotional impact	$\frac{(12+16+19+32+34+35)}{6}$	0, 5	5
Treatment concern	$\frac{(39+40+41)}{3}$	0, 5	5
Haemo-QoL-A Total	Sum of subscales (not individual items)	0, 30	30

Formula for transformation of the Haemo-QoL-A total raw score:

$$\text{Transformed Score} = \frac{\text{Actual raw total score}}{\text{Possible raw score range}} \times 100$$
